15.5. Efficacy Analyses

This study does not plan to test a formal hypothesis for any efficacy endpoint.

The endpoints of efficacy assessments are change in total and direct bilirubin, INR, creatinine, albumin, platelets, ALP, ALT, AST, and GGT from baseline to Week 48 (end of the study), change from baseline to Week 48 in CP score and components of the CP score, and change from

baseline to Week 48 in MELD and components of the MELD score. Analyses of change from Baseline to Week 48 (end of study) will be modelled between treatment groups using ANCOVA model with change from Baseline as the dependent variable, treatment group and randomization stratification factor as fixed effects and the baseline value as a covariate. The same analysis will be carried out using percentage change from Baseline as the dependent variable.

Analyses of change from Baseline to Week 48 (end of study) will be modelled between treatment groups using ANCOVA model with change from Baseline as the dependent variable, treatment group and randomization stratification factor as fixed effects and the baseline value as a covariate. The same analysis will be carried out using percentage change from Baseline as the dependent variable.

Summary statistics of the laboratory values will be provided by treatment group. The results, change from Baseline, and percentage change from Baseline values, as well as estimates of least-square (LS) means, standard errors (StdErr), and 2-sided 95% CIs, will be presented by treatment group. Estimates of the mean difference between treatment groups, the StdErr of the difference, and 2-sided 95% CI of the difference will also be presented.

Risk Scores: Changes from baseline in the MELD score and in CP score, C4, FGF-19 and plasma bile acids will be summarized and analyzed using the Wilcoxon Rank Sum Test. The median differences and 95% CI of the median differences between treatment groups will be constructed using Hodges-Lehmann estimate. If the median differences between treatments are not symmetrical around the median, the Sign Test may be used.

Shifts in MELD scores from Baseline will be reported by visit using the following categories: <10, 10 to <12, 12 to <13, 13 to <14, 14 to <15, and ≥ 15 .

CP class will be presented in shift tables showing the shift from baseline to each scheduled post-baseline visit by the count and percentage of patients within each shift classification.

Individual factors will be presented in a listing.

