14. EFFICACY ASSESSMENTS

14.1. Biochemical Measures of Disease Severity

14.1.1. Child-Pugh Score

Child-Pugh Score (Pugh 1973, Lucey 1997) is calculated and reported within the EDC system based on data entered into the eCRF by adding the scores from the 5 factors outlined in Table 12 and can range from 5-15. A total score of 5-6 is considered Grade A (mild, well-compensated disease); 7-9 is Grade B (moderate, significant functional compromise); and 10 and above is Grade C (severe, decompensated disease). Calculation of the CP Score includes Investigator assessments of ascites and hepatic encephalopathy, which may be assessed during the adverse event review at the scheduled visits, as well as total bilirubin, serum albumin, and prothrombin time, which will populate from the central laboratory.

Table 12: Child-Pugh Scoring System

Factor	Units	Points		
		1	2	3
Serum bilirubin	µmol/L	<34	34-50	>50
	mg/dL	<2.0	2.0-3.0	>3.0
Serum albumin	g/L	>35	28-35	<28
	g/dL	>3.5	2.8-3.5	<2.8
Prothrombin time	Seconds prolonged	0-3	4-6	>6
	INR	<1.7	1.7-2.3	>2.3
Ascites		None	Mild	Moderate-Severe
Hepatic encephalopathy ^a		0	Grade 1 or 2	Grade 3 or 4

^a Grade 0: normal consciousness, personality, neurological examination, electroencephalogram
Grade 1: restless, sleep disturbed, irritable/agitated, tremor, impaired handwriting, 5 cps waves
Grade 2: lethargic, time-disoriented, inappropriate, asterixis, ataxia, slow triphasic waves
Grade 3: somnolent, stuporous, place-disoriented, hyperactive reflexes, rigidity, slower waves
Grade 4: unrousable coma, no personality/behavior, decerebrate, slow 2-3 cps delta activity
(Pugh 1973, Lucey 1997), Vilstrup 2014

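### Section 15.5 applies percentage-change ANCOVA to Child-Pugh component points, so balanced fluctuation in ascites or encephalopathy is reported as a mean worsening

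*Protocol*

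**What the plan says.** The endpoint list in protocol section 15.5 includes "change from baseline to Week 48 in CP score and components of the CP score". The same list holds the laboratory values (bilirubin, albumin and INR among them) and the MELD score with its components. One model is given for the whole list: an ANCOVA of change on treatment arm and randomization stratum, adjusted for the baseline value. The next sentence is "The same analysis will be carried out using percentage change from Baseline as the dependent variable". The Synopsis says the same. LS means, standard errors and two-sided 95% intervals are required by arm and for the difference.

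Section 14.1.1 obtains the CP score "by adding the scores from the 5 factors outlined in Table 12 and can range from 5-15", and Table 12 gives each factor 1, 2 or 3 points. It also says: "Calculation of the CP Score includes Investigator assessments of ascites and hepatic encephalopathy". Those two factors have no laboratory value behind them.

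Three further statements in 15.5 bear on the point:

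- Totals are also sent to the Wilcoxon test, with Hodges-Lehmann estimates, in a sentence that opens "Changes from baseline in the MELD score and in CP score" and goes on to the PD markers. The components are not named there.
- A shift table is planned for CP class, not for the component points.
- "Individual factors will be presented in a listing".

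**The concern.** Percentage change needs a ratio scale. On the CP points, 1 stands for no ascites or Grade 0 encephalopathy. It is a label for the best category, not a quantity that can double. Because the denominator is the starting score, steps up from a low score weigh more than the same steps down from a high one. Mean percentage change therefore rises with fluctuation as well as with deterioration.

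The CP components are a stated secondary objective (section 6.2). If the plan is followed as written, the report will carry LS mean percentage changes for ascites and encephalopathy that can show worsening where the distribution of points has not moved. If one arm fluctuates more than the other, some of that will appear as a treatment difference.

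**Working it through.** The plan gives no figure for this analysis, so there is none to reproduce.

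**Inputs.** Points 1, 2, 3 (Table 12); percentage change = 100 × (post − base)/base; the ANCOVA of section 15.5. Baseline is taken as a whole-point score.

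**Balanced swaps.** For equal numbers moving a to b and b to a, mean change is 0 and mean percentage change is 100 × ½ × [(b − a)/a + (a − b)/b].

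| Swap | Up | Down | Mean change | Mean % change |
|---|---|---|---|---|
| 1 and 2 | +100% | −50% | 0 | +25.0% |
| 2 and 3 | +50% | −33.3% | 0 | +8.3% |
| 1 and 3 | +200% | −66.7% | 0 | +66.7% |

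The sign is no accident. If the set of scores is the same before and after, the ratios post/base multiply to 1, so their arithmetic mean is at least 1.

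**Dilution.** These means apply to the patients who swap. An arm with share f swapping 1 and 2 shows 25f%: f = 10%, 20%, 50% gives +2.5%, +5%, +12.5%.

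**Does the baseline covariate remove it?** Illustrative data, all assumed: 24 per arm (the plan has about 50 patients at 1:1), half at 1 and half at 2 points, a quarter in the second stratum; ANCOVA as in 15.5.

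| Scenario | Difference in change, points (95% CI) | Difference in % change (95% CI) |
|---|---|---|
| Both arms swap fully | 0 | 0 (each arm's LS mean is +25%) |
| One arm swaps fully, other stable | 0 (−0.30 to 0.30) | 25 (2.2 to 47.8) |
| Half of one arm swaps, other stable | 0 (−0.26 to 0.26) | 12.5 (−7.9 to 32.9) |

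Adjusting for baseline does not remove the artefact. Equal fluctuation and baseline mix cancel it in the difference, but not in the arm means.

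**A less extreme case.** Assume 40/30/30% at 1/2/3 points and a fraction of patients redrawn at random from that distribution. Mean post score is 0.4 + 0.6 + 0.9 = 1.9 and mean 1/base is 0.4 + 0.15 + 0.10 = 0.65. A redrawn patient's expected percentage change is then 1.9 × 0.65 − 1 = +23.5%. Redrawing 20% or 60% of an arm gives +4.7% or +14.1%, a gap of 9.4 points.

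For encephalopathy this mix cannot occur. Exclusion criterion 4 (section 8.3) bars current West Haven 2 or more, so baseline can only be 1 or 2 points. With a proportion p at 2 points, the expected percentage change is (1 + p)(1 − p/2) − 1 = p(1 − p)/2. For p = 15% to 30% and the same redraw rates, the gap is 0.4 × 6.4% to 0.4 × 10.5%, or about 3 to 4 points.

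**Precision.** Simulating the 40/30/30 case with 21 per arm (25 less 15% discontinuation) and 60% against 20% redrawn gives an average difference of 9 to 10 points and a 95% CI half-width of about 30. The interval excludes zero in about 7% of trials, against a nominal 5%.

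**Contrast with the total.** A 7 and 8 swap on the CP total gives 100 × ½ × (1/7 − 1/8) = +0.9%.

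**The case against.** The best case for the plan is that this matters little in practice. Three of the five factors have measured values, and bilirubin, albumin and INR are listed as such. With equal fluctuation in the arms the treatment difference is unaffected. Criterion 6 in section 8.3 excludes patients whose hepatic function is fluctuating or rapidly deteriorating before randomization. At this sample size the distortion of the contrast is small beside its interval. Nothing is formally tested, and efficacy is secondary to PK and safety. All of this stands, and it limits the size of the point. It does not rescue the output: the arm-level LS means remain biased, and two components have no scale other than points. Nor is this a detail left to a statistical analysis plan, because 15.5 states the model outright.

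Stronger readings are tempting but not supported:

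- A reader might infer that 15.5 contradicts itself by confining the factors to a listing. It says they will be listed; it does not say only listed. A listing can sit beside a model.
- A reader might take +25%, or a gap of about 10 points, as the expected bias in the treatment effect. The first is a mean among swapping patients. The second needs a 60% against 20% contrast that the protocol nowhere suggests, and a baseline mix impossible for encephalopathy.
- A reader might infer that ANCOVA on absolute change is equally broken. The swap examples give zero there.
- A reader might infer that two methods for the CP and MELD totals allow the result to be picked afterwards. The section commits to both and tests no hypothesis. What is missing is which one leads.

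**Conclusion.** The point holds for percentage change on the CP component points, and without qualification for ascites and encephalopathy. An arm with share f of patients swapping 1 and 2 points shows +25f% with no mean change in points. The between-arm difference is distorted only to the extent that fluctuation or baseline mix differs; under the assumed redraw rates that is about 3 to 4 percentage points for encephalopathy and up to about 10 for a component spread over all three categories. Those rates and baseline mixes are assumptions, not protocol figures. The consequence is a misleading LS mean, difference and interval for a secondary objective, with no effect on type I error.

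The same objection should not be carried over to the totals: the artefact on the CP total is trivial, and none has been shown for MELD. For these the only defect is that ANCOVA and Wilcoxon/Hodges-Lehmann are both assigned without an order.

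**What to change.** In section 15.5 and the Synopsis:

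1. Exclude the CP component points from the percentage-change analysis.
2. Report ascites and encephalopathy points by shift table from baseline to each scheduled visit, as already planned for CP class. Add a rank or ordinal comparison between arms if the data allow. A proportional-odds model should not be mandatory: with about 25 patients per arm and sparse encephalopathy categories it may not be estimable.
3. Analyse bilirubin, albumin and INR on their measured scales, as already listed.
4. State whether ANCOVA or Wilcoxon/Hodges-Lehmann leads for the CP and MELD totals, and call the other supportive.
5. Say that the listing of individual factors is additional to these analyses.

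The cost is a change of wording and the loss of one set of outputs. No new data are needed, and sample size and visits are unaffected.

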9.4. Randomization and Blinding

9.4.1. Methods of Assigning Patients to Treatment Groups

This study will be conducted in a double-blind, placebo-controlled manner. Enrolled patients who meet all eligibility requirements will be randomized in a 1:1 ratio to 1 of 2 treatment groups: placebo or OCA based on a predefined randomization code (generated by Sponsor or designee) using an interactive web response system (IWRS), which the Sponsor intends will serve as a computer-based patient registration system at Screening and Day 1.

Randomization will be stratified by CP class (CP-B or CP-C). Baseline MELD scores will be monitored on an ongoing basis to ensure adequate distribution of MELD scores. The IWRS will serve as the investigational product inventory and management system and may be integrated with the study database.

The Investigator or designee will be required to register the patient in the IWRS and may be prompted to provide patient data necessary to properly randomize and allocate the patient to treatment. A randomization number will be assigned and investigational product (OCA or

placebo) dispensing information will be provided (eg, bottle numbers allocated) while maintaining the study blind.

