15.6. Additional Efficacy Analyses

Analyses of changes in liver stiffness (TE) and liver fibrosis (ELF [HA, P3NP, and TIMP-1]) will be summarized and analyzed using the same methodology specified for the key secondary analyses of change in bilirubin.

The following clinical endpoints will be captured in the study:

- Time to death (all cause)
- Time to liver-related death
- Time to liver transplant
- MELD score ≥ 15 (for patients with MELD ≤ 12 at baseline)
- Hospitalization (as defined by a stay of 24 hours or greater) for new onset or recurrence of:
 - Time to variceal bleed
 - Time to hepatic encephalopathy (as defined by a West Haven score of ≥ 2)

- Time to spontaneous bacterial peritonitis (confirmed by diagnostic paracentesis)
- Time to uncontrolled ascites (diuretic resistant ascites requiring therapeutic paracentesis at a frequency of at least twice in a month).

The incidence and time to first occurrence of any above listed clinical events will be summarized by treatment group using the log rank test stratified by the randomization stratification factor. KM estimates of the distribution of the time-to-event will be tabulated and graphed by treatment group. The tabulation will include the KM methodology using 25th, 50th (median), and 75th percentiles with associated 2-sided 95% confidence intervals (CIs), as well as percentage of censored observations. The number and percent of patients censored and with events will be presented. The hazard ratio and 2-sided 95% CI will be estimated based on a Cox regression model stratified by randomization strata.

In addition, the incidence and time to each of the above clinical events, and the incidence and time to occurrence of hepatocellular carcinoma (HCC) will be summarized by treatment group using the same methods as defined above.

Full details regarding additional efficacy analyses will be detailed in the SAP.

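### The rank analyses in Section 15.5 leave out the Child-Pugh randomization stratum, so their 95% intervals may be wider than needed, chiefly for C4, FGF-19 and plasma bile acids

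*Protocol*

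**What the plan says.** Section 9.4.1 of the protocol stratifies the 1:1 randomization by CP class, B or C. Section 15.2 plans about 50 patients, at least 20% of them CP-C.

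Section 15.5 contains two between-group analyses.

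- **ANCOVA of change to Week 48.** It has "treatment group and randomization stratification factor as fixed effects and the baseline value as a covariate". Its listed endpoints are liver biochemistry and related laboratory measures, the MELD score with its parts, and "change from baseline to Week 48 in CP score and components of the CP score". C4, FGF-19 and plasma bile acids are not on that list.
- **Rank analysis, under Risk Scores.** It covers change in MELD and CP score, and adds that "C4, FGF-19 and plasma bile acids will be summarized and analyzed using the Wilcoxon Rank Sum Test". The accompanying "95% CI of the median differences between treatment groups will be constructed using Hodges-Lehmann estimate". No stratum or covariate is named.

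Section 15.6 analyses clinical events with a "log rank test stratified by the randomization stratification factor" and a Cox model stratified the same way. Sections 15 and 15.5 both state that no formal hypothesis is tested. Section 15 adds that 95% intervals for the treatment difference will be shown. Section 6.2 makes the effect on C4, FGF-19 and plasma bile acids a secondary objective.

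**The concern.** A plain rank-sum test, and the Hodges-Lehmann interval obtained by inverting it, rank CP-B patients against CP-C patients and treat the labels as exchangeable across the whole trial. The trial balances treatment within each class. If the classes differ in how much they change, that difference is counted as noise in the plain interval, although the design has already removed it from the treatment comparison. The other modelled or tested efficacy comparisons in Section 15 carry the stratum. This one does not, and no reason is given.

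Because the study presents intervals rather than tests, what is at stake is the width of the reported interval. It matters most for the three pharmacodynamic markers, for which the rank analysis is the only between-group method expressly named.

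**Working it through.** **Inputs from the protocol.** Total 20 + 10 + 20 = 50 patients, which reproduces the stated sample size and gives 25 per arm at 1:1. The CP-C floor is 0.20 × 50 = 10, leaving 40 CP-B. The protocol states no power or precision for the rank analysis, so there is no figure of its own to reproduce on that point.

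**Assumptions.**
- Changes are normal with within-class SD 1.
- The CP-C minus CP-B difference in mean change, d, runs from 0 to 2 SD. The protocol does not give it.
- Randomization uses permuted blocks of 4 within class.
- The treatment effect for the power columns is 0.82 SD.

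**Approximate formula.** With CP-C share p, the pooled variance is 1 + p(1 − p)d², while the variance relevant to a comparison stratified 1:1 is 1. The plain interval is therefore wider by about √(1 + p(1 − p)d²). With p = 0.2, p(1 − p) = 0.16:
- d = 0.5: √1.04 = 1.02
- d = 1: √1.16 = 1.08
- d = 1.5: √1.36 = 1.17
- d = 2: √1.64 = 1.28

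**Simulation, 40 CP-B and 10 CP-C** (3,000 trials per row for intervals, 40,000 for size and power). The plain Wilcoxon and Hodges-Lehmann methods are compared with van Elteren (weights 1/(n_h + 1)) and its within-class Hodges-Lehmann interval. Each pair is plain / stratified.

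| d (SD) | Mean 95% width | Ratio | Coverage | Size at nominal 0.05 | Power |
|---|---|---|---|---|---|
| 0 | 1.163 / 1.177 | 0.99 | 95.4% / 95.5% | 0.049 / 0.049 | 79% / 78% |
| 0.5 | 1.185 / 1.176 | 1.01 | 96.1% / 95.7% | 0.047 / 0.050 | 78% / 78% |
| 1 | 1.251 / 1.174 | 1.07 | 96.3% / 95.3% | 0.037 / 0.050 | 74% / 78% |
| 1.5 | 1.356 / 1.181 | 1.15 | 97.3% / 95.2% | 0.025 / 0.047 | 68% / 78% |
| 2 | 1.466 / 1.176 | 1.25 | 98.2% / 95.4% | 0.018 / 0.048 | 61% / 78% |

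The simulated ratios track the formula and are slightly smaller. The plain interval never under-covers.

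**Larger CP-C share.** The protocol's 20% is a floor. At d = 1 the formula gives √(1 + 0.24) = 1.11 for 40% CP-C and √(1 + 0.25) = 1.12 for 50%. In simulation with 25 patients per class and d = 1, size is 0.030 against 0.052 and power 71% against 79%.

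**Dropout.** At 15% loss, 50 × 0.85 = 42.5. With 34 CP-B and 9 CP-C and d = 1, power is 67% against 72%, so the pattern does not change.

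**Cost of stratifying when class is irrelevant (d = 0).** Power is 78.8% against 77.8%, a loss of 1 point. The width ratio is 1.177 / 1.163 = 1.012, or about 2% from the widths rounded to 1.18 and 1.16.

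**The case against.** The strongest reply is that this is an efficiency preference in a descriptive analysis. Its parts, and what stands of each:

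- **The analysis stays valid.** A reader might infer that the reference distribution is wrong and the results unsound. The check does not support that: the error runs only in the conservative direction, and it vanishes when class does not predict change. This stands.
- **Power is not the yardstick.** A reader might pick out the drop from 78% to 61%. It needs a 2 SD class difference in change, which nothing in the protocol supports, and no efficacy test is planned. Change scores already remove stable level differences between the classes. This stands, and the size is therefore expressed here as interval width.
- **MELD and CP score are covered.** A reader might infer that all five measures lack a stratified analysis. The ANCOVA adjusts MELD and CP score for both stratum and baseline. For them the rank analysis is a second look, and two methods can differ for many reasons. This stands.
- **The markers may be covered too.** Section 15.5 promises least-squares means and differences for laboratory values, and Table 11 lists the three markers as laboratory analytes. This stands only in part, because they are absent from the endpoints named for the ANCOVA.
- **A SAP could settle it.** Sections 15.3 and 15.6 defer detail to a SAP, which is not at hand. But Section 15.5 names both the test and the interval, and a SAP that follows it literally would omit the stratum.

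On the other side, Section 5.4.2 predicts plasma OCA 8.0-fold higher in CP-B and 13-fold in CP-C (liver 1.5- and 1.7-fold). That makes a class difference in marker response plausible, but it does not quantify d.

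**Conclusion.** The point holds as a low-severity inefficiency. The rank test and Hodges-Lehmann interval in Section 15.5 do not carry the randomization stratum that the protocol's other modelled or tested efficacy comparisons include. The consequence is a 95% interval that may be wider than necessary. At 20% CP-C the excess is negligible up to a 0.5 SD class difference in change, about 7% at 1 SD, 15% at 1.5 SD and 25% at 2 SD, and more with a larger CP-C share.

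These figures rest on normal, complete data and an assumed range for a class difference that the protocol does not state. The practical cost falls mainly on C4, FGF-19 and plasma bile acids.

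**What to change.** In Section 15.5, Risk Scores, replace the plain rank-sum test by the van Elteren test stratified by randomized CP class. Replace the Hodges-Lehmann estimate by its stratified form, obtained by inverting the van Elteren statistic or pooling within-class pairwise differences, with its 95% interval. A rank ANCOVA with CP class and baseline is a reasonable alternative, since van Elteren does not adjust for baseline and the CP-C stratum may hold only about 5 patients per arm.

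The change is one sentence, needs no new data and uses standard software. If the SAP already specifies a stratified version, aligning the protocol wording is enough.

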7. INVESTIGATIONAL PLAN

7.1. Overall Study Design

This Phase 4, randomized, double-blind, placebo-controlled study will evaluate the PK and safety of OCA treatment in patients with PBC and moderate to severe hepatic impairment defined as CP-B and CP-C including a broad distribution of MELD scores (ranging from 6 to 24). Approximately 50 patients (including at least 20% of patients with CP-C) will be enrolled in the study. Patients will be screened ≥ 14 days but not more than 28 days prior to entering the study (Day 1). Patients who meet all eligibility requirements will be randomized in a 1:1 ratio to 1 of 2 treatment groups: Placebo or OCA. Randomization will be stratified by CP class. Baseline MELD scores will be monitored on an ongoing basis to ensure adequate distribution of MELD scores.

[figure not shown]
Following completion of safety assessments and laboratory specimen collection, blinded investigational product will be dispensed with instruction to begin dosing the same day (Day 1) at OCA 5 mg or placebo once weekly.

Double-Blind Treatment Period: During the 48-week treatment period, an initial safety visit will occur at Week 3. After the Week 6 Visit, subsequent clinic visits will occur approximately every 6 weeks for the assessment of safety, tolerability, PK, and PD. Titration may be considered as early as the Week 12 Visit (see [Section 7.3](#)). Fasting PK assessments will be performed in all patients participating in the study on Day 1, Week 6, and Week 36. Serial PK sampling (which also includes a fasted PK assessment) will be performed at Week 12, 18, 24, 30, and 48.

Patients who have completed their 48-week, double-blind treatment period will continue double-blind treatment until all randomized patients have completed their 48-week treatment period and the database for that period is locked. An open-label extension study in which all patients receive OCA will be considered following review of blinded safety and PK data.

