7.2. Number of Patients

Approximately 50 patients will be enrolled in this study.

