15. STATISTICAL METHODS AND ANALYSES

Individual patient data obtained from electronic case report forms (eCRFs), central laboratories, external sources, and any derived data will be presented in data listings by patient. All data listings that contain an evaluation date will contain a relative study day. Pre-treatment and on treatment study days are numbered relative to the day of the first dose of investigational product which is designated as Day 1.

All output will be incorporated into Microsoft Word rich text format (.rtf) files, sorted and labeled according to the International Conference on Harmonisation (ICH) recommendations, and formatted to the appropriate page size(s).

Tabulations will be produced for appropriate demographic, Baseline, efficacy, and safety parameters.

For categorical variables, summary tabulations of the number and percentage of patients within each category (with a category for missing data) of the parameter will be presented. Percentage calculations will be based on non-missing data, unless otherwise specified. Percentages are rounded to 1 decimal place, unless otherwise specified.

For continuous variables, the number of patients, mean, standard deviation (SD), standard error of the mean (SEM), median, minimum, and maximum values will be presented. The precision of summary statistics, unless otherwise specified will be as follows: mean and median to 1 more decimal place than the raw data, and SD and SEM to 2 decimal places more than the raw data. In general, the decimal places should not exceed 3 decimal places unless appropriate. Confidence intervals (CIs) will be provided and will be rounded to 1 decimal place, unless otherwise specified.

Time-to-event data will be summarized using Kaplan-Meier (KM) methodology using 25th, 50th (median), and 75th percentiles with associated 2-sided 95% CIs, as well as percentage of censored observations.

There will be no formal hypothesis testing in this study. However, summary statistics for each treatment group will be presented, as well as 95% CIs for the difference between the treatment groups.

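### Section 15.5 names a Sign Test that cannot compare two independent arms, and its MELD shift table cannot show worsening in patients who enter at 15 or more

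*Protocol*

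**What the plan says.** Protocol Section 9.4.1 describes a parallel design: patients "will be randomized in a 1:1 ratio to 1 of 2 treatment groups: placebo or OCA". Nothing in it pairs or matches patients across arms. Section 7.2 gives the size: "Approximately 50 patients will be enrolled in this study", so about 25 per arm.

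Under Risk Scores, Section 15.5 states: "Changes from baseline in the MELD score and in CP score, C4, FGF-19 and plasma bile acids will be summarized and analyzed using the Wilcoxon" rank-sum test. It plans a Hodges-Lehmann estimate and 95% CI for the difference between treatment groups, and then adds: "If the median differences between treatments are not symmetrical around the median, the Sign Test may be used".

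The same section assigns an ANCOVA (treatment, stratification factor, baseline value) to a list of endpoints. That list includes MELD and Child-Pugh change. It does not include C4, FGF-19 or bile acids.

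The section continues: "Shifts in MELD scores from Baseline will be reported by visit using the following categories". There are six bands: below 10, 10 to below 12, single-point bands at 12, 13 and 14, and an open band from 15. Section 7.1 describes the population as "including a broad distribution of MELD scores (ranging from 6 to 24", and Section 8.2 makes the same range an inclusion criterion.

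On inferential status, Section 15 states: "There will be no formal hypothesis testing in this study".

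**The concern.** The Sign Test asks whether the median of one set of differences is zero. Those differences must come from one sample (each patient's own change) or from genuine pairs. With two unpaired arms it can test change over time within an arm, but not OCA against placebo, and the secondary objectives in Section 6.2 are framed as OCA compared with placebo. The symmetry condition is also misplaced. It is an assumption of the Wilcoxon signed-rank test for paired data. The sentence seems to carry paired-data reasoning into a two-sample analysis.

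The exposure is greatest for C4, FGF-19 and plasma bile acids, which are secondary objectives too. If the Sign Test replaced the rank-sum test for them, the only test reported would not be a treatment comparison.

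The shift table raises a separate matter. The trial deliberately enrols patients up to MELD 24, yet the table cannot register any movement at or above 15.

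**Working it through.** The plan gives no power or alpha for this analysis, so there is no figure to reproduce.

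**Sign Test: what it would measure**

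Inputs: 50 patients in a 1:1 ratio, so 50 / 2 = 25 per arm (Sections 7.2 and 9.4.1). Assumed for illustration: normally distributed changes, SD 3, and the same average drift in both arms, so no treatment effect. Only the ratio of drift to SD matters.

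Rejection rule for a two-sided sign test on 25 changes at 0.05: reject when 7 or fewer, or 18 or more, are positive. With no drift the exact rejection rate is 2 × (1 + 25 + 300 + 2,300 + 12,650 + 53,130 + 177,100 + 480,700) / 2^25 = 2 × 726,206 / 33,554,432 = 4.3%.

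Simulated rejection rates, 4,000 runs per row:

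| Common drift (SD) | Sign test within one arm | Rank-sum between arms |
|---|---|---|
| 0 | 4.0% | 4.9% |
| 0.17 | 8.3% | 5.0% |
| 0.33 | 24.4% | 5.0% |
| 0.5 | 47.5% | 4.5% |
| 1.0 | 96.4% | 5.0% |

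The rank-sum test holds its level at every drift tried. The sign test responds to the drift, although the arms do not differ. Section 5.5 describes PBC as chronic and progressive, so drift common to both arms is plausible for MELD and Child-Pugh.

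The other way to apply the test is to pair OCA and placebo patients arbitrarily. On one simulated data set (25 per arm, true means 0 and 2, SD 3, rank-sum p = 0.36), 5,000 random pairings gave sign-test p-values from 0.015 to 1.0. The result then depends on the pairing, which the design does not supply.

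**The symmetry condition**

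The two-sample Hodges-Lehmann estimate is the median of all 25 × 25 = 625 between-arm differences. Its usual interval rests on the arms differing by a location shift, not on either arm being symmetrical. The rank-sum test does not need symmetry either. A SAP could define how symmetry is judged, but that would not make it a relevant condition.

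**MELD shift table**

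Input: eligible scores 6 to 24, which is 24 − 6 + 1 = 19 whole-number values.

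| Band | Eligible scores | Count |
|---|---|---|
| Below 10 | 6 to 9 | 4 |
| 10 to below 12 | 10, 11 | 2 |
| 12 | 12 | 1 |
| 13 | 13 | 1 |
| 14 | 14 | 1 |
| 15 and above | 15 to 24 | 10 |

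The top band holds 10 / 19 = 53% of eligible values. A patient entering there can stay or move down, never up, and a fall from 24 to 15 appears as no shift. The categorical MELD event in Section 15.6 does not fill the gap, because it counts a score of 15 or more only in patients at 12 or less at baseline.

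The 53% is a share of score values. The number of patients depends on a baseline distribution that the protocol does not give. For illustration, among 50 patients, 20% would be 10 patients and 50% would be 25.

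**The case against.** The strongest reply is that little hangs on either item.

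The Sign Test is optional, and no efficacy hypothesis is formally tested. A reader might infer that, if the fallback is used, MELD and Child-Pugh change are left without a treatment comparison. The protocol does not support that. Section 15.5 separately specifies an ANCOVA for both, with a between-group mean difference and 95% CI. The Hodges-Lehmann sentence is also unconditional, so on its face that interval would be reported for all five measures. This stands. It limits the consequence but does not make the sentence right.

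On the shift table, MELD change is also analysed as a continuous variable. Section 13.1.1.4 lists a persistent 3-point MELD rise among the adverse events of special interest, with no upper limit on the baseline score. Worsening above 15 is therefore captured elsewhere, and one descriptive table loses it. The single-point bands have a visible purpose too, since they follow the approach to the Section 15.6 event. Both replies stand. They explain the detail below 15 but not the lack of it above.

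A reader might also want one main method named for MELD and Child-Pugh, or the rank-sum test stratified by Child-Pugh class. Neither is an error here. With no formal testing, ranking the methods can be left to the SAP. An unstratified rank-sum test remains a valid comparison after stratified randomisation, and the ANCOVA already carries the factor.

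**Conclusion.** Both points hold, with modest consequences.

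The Sign Test sentence is wrong as written: the test does not fit two independent arms, and its condition belongs to a different procedure. That conclusion needs no assumption beyond the parallel design. The simulated rates rest on the assumed normal changes and only illustrate it. C4, FGF-19 and bile acids are the most exposed, because rank-sum with Hodges-Lehmann is the only between-arm method the section names for them. The ANCOVA paragraph is repeated in general terms, but the endpoint list before it omits these markers.

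The MELD shift table hides all movement among patients at 15 or more, which is 10 of 19 eligible scores counted in whole points. It would be tempting to say that the table is blind to the sickest half of the population. The protocol does not support this: it seeks a broad spread, not an even one, and gives no baseline distribution. These patients are counted in the table; only their movement is lost.

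**What to change.** 1. Delete the Sign Test sentence from Section 15.5. Keep the rank-sum test with the Hodges-Lehmann difference and 95% CI, with no symmetry condition.

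2. Keep the bands below 15 and split the top one into several bands that cover 15 to 24 and above. The cut-points are the sponsor's choice. For illustration, 15 to below 18, 18 to below 21, 21 to below 25, and 25 or more would hold 3, 3, 4 and 0 of the eligible scores. Every eligible entry score would then have a band above it, so worsening could be seen.

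The cost is one deleted sentence, one revised list of categories and one table shell. Trial conduct and data collection do not change.
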